6.1. General Methods

All analyses and outputs will be produced using SAS® version 9.4 or later. Continuous variables will be summarized using the number of observations (n), mean, standard deviation (SD), median, minimum, and maximum. Categorical variables will be summarized using frequency counts (n), and percentages.

All relevant subject data will be included in listings. All subjects entered the database will be included in subject data listings. All by visit summaries will use the nominal visit. Unscheduled visits will not be summarized but will be included in the listings.

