6.4. Visit Windows

The following visit windows will be used in the summarization or analysis of safety laboratory, vital signs, ECG, and physical exam data. If more than 1 data point falls within the window, then the data point

This document is confidential.

closest to the target day will be used. If there are 2 data points equidistant to the target day, one high and one low, then the high data point will be used. Visit windowing will not be applicable to follow-up visits.

If Baseline is Day 1, then:

Month 1 (target day = 29) 2 - 42

Month 2 (target day = 57) 43 - 70

Month 3 (target day = 85) 71 - 98

Month 4 (target day = 113) 99 - 126

Month 5 (target day = 141) 127 - 154

Month 6 (target day = 169) 155 - 182

Month 7 (target day = 197) 183 - 210

Month 8 (target day = 225) 211 - 238

Month 9 (target day = 253) 239 - 266

Month 10 (target day = 281) 267 - 294

Month 11 (target day = 309) 295 - 322

Month 12 (target day = 337) 323 and above (and not a follow-up visit)

For all efficacy and safety scales a modified last observation carried forward (LOCF) approach will be used to reassign Early Termination visits. Early Termination visits will be assigned to the next scheduled visit (per Schedule of Assessments for the parameter) after a subjects' latest scheduled visit before early termination.

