9.6. ECG

The following ECG data will be collected at Baseline, Months 1, 3, 6, 9 and 12:

- PR interval (msec)
- QRS interval (msec)
- QT interval
- QTc interval (msec)
- Overall ECG result (Normal; Abnormal, Not Clinically Significant; Abnormal, Clinically Significant).

An ECG is optional at unscheduled visits, per the investigator's discretion.

The actual ECG results along with change from baseline will be summarized at each visit. Shift (<=450, >450 to <= 480, > 480 to <= 500, >500) from baseline in QTc interval will be summarized by visit. ECG outliers for QTc interval (change from baseline>30 to <=60, >60), PR interval (>25% increase change from baseline,>200, >25% increase change from baseline and PR>200) and QRS interval (>25% increase change from baseline,>200, >25% increase change from baseline and QRS>200) will be summarized by visit and overall. All ECG data will be presented in a listing.

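### The overall ECG and heart-rate outlier rows can miss subjects whose only out-of-limit value came at an unscheduled visit, or at an early-termination visit displaced by the window rule

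*SAP*

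**What the plan says.** SAP 6.1 sets two general rules: "All by visit summaries will use the nominal visit" and "Unscheduled visits will not be summarized but will be included in the listings". It makes no exception for tables that are not by visit.

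SAP 6.4 sets a different basis for four kinds of data: "The following visit windows will be used in the summarization or analysis of safety laboratory, vital signs, ECG, and physical exam data". Where several values share a window, the one "closest to the target day will be used". For ties: "If there are 2 data points equidistant to the target day, one high and one low, then the high data point will be used". The same section moves an ET visit to the next scheduled visit, but only for the efficacy and safety scales. ET laboratory, vital-sign, ECG and physical-examination values simply fall into whichever window contains their study day. Follow-up visits are not windowed.

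SAP 9.6 allows an ECG at an unscheduled visit if the investigator wants one. It says that outliers in QTc change, PR and QRS "will be summarized by visit and overall". SAP 9.5 plans the same two levels for heart rate, with low limits (fall of more than 25%, below 50) and high limits (rise of more than 25%, above 100). The laboratory, HbA1c, cholesterol, z-score and QTc shifts are planned by visit only. Section 10 of the SAP records that the windowing and both outlier tables were added after database lock.

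**The concern.** A reader takes an overall outlier row to mean the share of subjects who ever crossed the limit. Under SAP 6.1 and 6.4 it can mean something narrower: the share who crossed it in the values that survived selection. The values at risk of removal include ECGs or pulse readings taken off schedule, possibly because something was wrong, and readings taken as a subject leaves the study. No any-time or worst-post-baseline rule brings them back into a table. Long-term safety and tolerability is the primary objective, so a rule that can only remove positive findings from an overall safety count matters even when the tables are descriptive.

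**Working it through.** The plan states no figure on this point, so the window grid is the only thing to reproduce.

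**1. Grid (SAP 6.4).** For month m, target t = 28m + 1 and the window runs from t − 14 to t + 13. Month 1 instead starts at Day 2, and Month 12 has no upper limit. Month 3 gives 28 × 3 + 1 = 85 and Days 71 to 98, matching "Month 3 (target day = 85) 71 - 98". All twelve windows match. Month 9 has target 253 and Days 239–266.

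**2. Example.** A scheduled ECG on Day 253 is normal. The ET ECG on Day 258 shows a QTc change above 60. Both fall in Days 239–266. The distances are |253 − 253| = 0 and |258 − 253| = 5, so Day 253 is kept. If this was the subject's only large change, the subject is missing from both the Month 9 row and the overall row.

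**3. Reach of the window rule for ET values.** Inputs are the SAP 6.4 windows, the protocol Table 2 schedule (vital signs monthly; ECG and laboratory tests at Months 1, 3, 6, 9 and 12) and its ±3-day tolerance. Assumption: all scheduled visits before ET took place, either on target or all 3 days off. An ET value on day d is displaced by an earlier scheduled value on day s in the same window when |d − t| > |s − t|. Possible ET days are 2 to 336, which is 335 days, less the scheduled visit days.

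| Scheduled visits | Days lost per window | Vital signs | ECG and laboratory |
|---|---|---|---|
| On target | 13 (t + 1 to t + 13) | 11 × 13 = 143; 143/324 = 44% | 4 × 13 = 52; 52/331 = 16% |
| 3 days late | 10 (t + 4 to t + 13) | 110/324 = 34% | 40/331 = 12% |
| 3 days early | 10 (t + 4 to t + 13) | 110/323 = 34% | 40/330 = 12% |

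Ties with an ET value arise only in the last row, on one day per window (t + 3): 11 days for vital signs and 4 for ECG and laboratory tests.

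**4. Unscheduled values.** If SAP 6.1 governs, all of them leave the summaries. If SAP 6.4 is read as admitting them, take a 28-day window (Months 2–11) that also holds a scheduled value. With that visit on target, an extra value is dropped on 27 of the 27 other days. With the visit 3 days off, it is dropped on 21, ties on 1 and replaces the scheduled value on 5. In a window with no scheduled value, such as an ECG in Month 4, it would be kept.

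**5. Direction.** Removing a value can take a subject out of the count of those who ever crossed a limit and can never add one, so the count errs only downward. The rate follows, because an ET value is displaced only when another value from the same subject is kept. The one exception is a subject whose only post-baseline values are unscheduled and within limits, who would also leave the denominator (SAP 12.2.5.2).

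**The case against.** The strongest reply is that the loss is not certain. In SAP 6.1 the sentence on unscheduled visits directly follows the one on by-visit summaries and may be meant only for those. Overall is undefined, so a programmer could take it to cover all values. SAP 6.4 is the later and more specific rule, and it foresees several values in a window. On the nominal-visit basis of SAP 6.1 alone, ET is a scheduled column and its value would be summarized. All of this is fair, but it shows that the two sections conflict and that the text does not secure the reading needed for a safety count.

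The second reply is that there are back-ups. Every value is listed. Protocol 12.4 requires an AE record when an abnormal value is an SAE or leads to stopping study drug, and protocol 12.2.1 adds other triggers. Yet 12.4 also leaves clinically significant changes in laboratory values, blood pressure and pulse to the investigator's judgement. Neither listings nor AE tables give the rate of subjects beyond a numeric limit.

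A reader might also infer more than the documents support:

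- *That overall shift, laboratory or blood-pressure rates are biased.* No such rows are planned. A displaced ET laboratory value, or an ET QTc above 500 on Day 95 after a normal Day 85 ECG, is lost from a by-visit shift table only.
- *That every ET value is lost.* Loss needs a nearer value in the same window. ET values on the rating scales are kept by reassignment.
- *That the tie rule selects the reassuring value.* High may mean the later day. Even if it means the higher value, that is the cautious choice for the ECG outlier limits, which are all increases. Among the overall rows only low heart rate could suffer, and only on exact ties.
- *That rates of adverse events of special interest are affected.* Those tables come from reported AEs, not windowed values.

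**Conclusion.** The point stands for the overall rows of the ECG and heart-rate outlier tables. As written, those rows can omit a subject whose only out-of-limit value was unscheduled, or was an ET value displaced by a nearer scheduled one, and the resulting count can only be too low. The by-visit shift tables can lose the same values, but they make no ever-crossed claim.

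The number of subjects affected is unknown. The 34–44% (vital signs) and 12–16% (ECG) are shares of possible ET days. They assume scheduled visits on the SAP's 28-day grid or 3 days off it, and would change if visits followed calendar months. They do not forecast bias in any rate. The conclusion also assumes that SAP 6.1 or 6.4 applies to the overall rows. The SAP says nothing to exempt them.

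The tables are descriptive and SAP section 14 lists them as post hoc, so no test is at risk. The change should be made because the undercount is one-directional, concerns the primary objective and is easy to remove.

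**What to change.** - Keep the by-visit tables as planned.
- State in SAP 9.5 and 9.6 that the overall outlier rows count a subject if any post-baseline value (scheduled, unscheduled or ET) meets the criterion.
- Reconcile SAP 6.1 with 6.4: say which governs laboratory, vital-sign, ECG and physical-examination data, and whether unscheduled values may enter a window.
- Say whether high in the tie rule means the later day or the higher value. If the higher value, replace it with the worse value in the direction of concern for each parameter, for example the lower one when assessing heart rate below 50.
- Optionally, add a shift from baseline to worst post-baseline value. This is a preference, not the correction of an error.

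The windowing and both outlier tables were themselves added after database lock, so the clarification should be dated and labelled in the same way. The cost is SAP wording and a little extra programming, with no new data. The downside for the sponsor is that the overall outlier rates may come out slightly less favourable.

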6.2. Key Definitions

Treatment emergent adverse events (TEAEs) are defined as any adverse events that start or increase in intensity on or after the first dose of open-label treatment on Day 1.

Duration of exposure is defined as (Date of Last Dose – Date of First Dose) +1. If date of last dose is unknown, then the date of last clinical visit will be used to impute the date of last dose.

Baseline is defined as the last measurement taken before the first dose of open-label treatment on Day 1.

Change from baseline will be calculated for the post-baseline assessment as post-baseline value – baseline value.

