- 15) Subjects with a lifetime history of bipolar disorder type I or II, dementia, schizophrenia, or any other psychotic disorder.
- 16) Inability to swallow tablets.
- 17) Subjects with a known hypersensitivity to ecopipam or any of its excipients.
- 18) Any subject who in the opinion of the investigator is not a suitable candidate for the study.

Investigational product, dosage and mode of administration:

Ecopipam HCl will be supplied as 12.5-, 37.5-, 50-, 75-, and 100-mg tablets. The target dose is 2 mg/kg via oral administration.

Subjects will be dosed according to the following weight bands to better achieve the 2 mg/kg/day target dose: $\geq 18-\leq 23$ kg, $\geq 23-\leq 34$ kg, $\geq 34-\leq 44$ kg, $\geq 44-\leq 68$ kg, $\geq 68-\leq 83$ kg, ≥ 83 kg.

During the 4-week titration period, the following ecopipam HCl doses will be administered for each of the weight bands:

- Those who weigh ≥18-≤23 kg will titrate from 12.5 mg daily to 37.5 mg daily: 12.5 mg during Week 1, 25 mg during Week 2, and 37.5 mg during Weeks 3 and 4.
- Those who weigh >23-\le 34 kg will titrate from 12.5 mg daily to 50 mg daily: 12.5 mg during Week 1, 25 mg during Week 2, 37.5 mg during Week 3, and 50 mg during Week 4.
- Those who weigh >34- \leq 44 kg will titrate from 12.5 mg daily to 75 mg daily: 12.5 mg during Week 1, 25 mg during Week 2, 50 mg during Week 3, and 75 mg during Week 4.
- Those who weigh >44-≤68 will titrate from 25 mg daily to 100 mg daily: 25 mg during Week 1, 50 mg during Week 2, 75 mg during Week 3, and 100 mg during Week 4.
- Those who weigh >68- \leq 83 kg will titrate from 25 mg daily to 150 mg daily: 25 mg during Week 1, 50 mg during Week 2, 100 mg during Week 3, and 150 mg during Week 4.
- Those who weigh >83 kg will titrate from 25 mg daily to 200 mg daily: 25 mg during Week 1, 50 mg during Week 2, 100 mg during Week 3, and 200 mg during Week 4.

During the 52-week treatment phase, the following ecopipam doses will be administered for each of the weight bands:

- Those who weigh $\ge 18 \le 23$ kg will receive 37.5 mg daily.
- Those who weigh >23-\le 34 kg will receive 50 mg daily.
- Those who weigh >34-≤44 will receive 75 mg daily.
- Those who weigh >44-≤68 kg will receive 100 mg daily.
- Those who weigh >68-\le 83 kg will receive 150 mg daily.
- Those who weigh >83 kg will receive 200 mg daily.

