8.3. Subject Withdrawal Criteria

The Investigator or subject themselves may stop study treatment at any time for safety or personal reasons.

Any subject with a CDRS-R assessment indicative of the onset of a new depressive episode at any visit can be discontinued from study participation at the discretion of the Investigator. Any subject with a new positive response on questions 4 and/or 5 of the C-SSRS will be immediately discontinued and evaluated for risk. Dosing may be restarted at the discretion of the Investigator following consultation with the Sponsor or its designee.

Where possible, a subject who discontinues treatment will undergo the protocol-specified end-of study procedures at the time of discontinuation. Date and reason(s) of premature discontinuation will be described on the CRF. In addition, the date of last dose of study treatment will be recorded on the Study Treatment Dosing CRF.

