10.5. Administration

Ecopipam HCl will be supplied as 12.5-, 37,5-, 50-, 75-, and 100-mg tablets. The target dose is 2 mg/kg via oral administration.

During the 4-week titration period, the following ecopipam HCl doses will be administered for each of the weight bands:

- Those who weigh ≥18-≤23 kg will titrate from 12.5 mg daily to 37.5 mg daily: 12.5 mg during Week 1, 25 mg (two 12.5-mg tablets) during Week 2, and 37.5 mg during Weeks 3 and 4.
- Those who weigh >23- \leq 34 kg will titrate from 12.5 mg daily to 50 mg daily: 12.5 mg during Week 1, 25 mg (two 12.5-mg tablets) during Week 2, 37.5 mg during Week 3, and 50 mg during Week 4.
- Those who weigh >34- \leq 44 kg will titrate from 12.5 mg daily to 75 mg daily: 12.5 mg during Week 1, 25 mg (two 12.5-mg tablets) during Week 2, 50 mg during Week 3, and 75 mg during Week 4.
- Those who weigh >44- \leq 68 kg will titrate from 25 mg daily to 100 mg daily: 25 mg (two 12.5-mg tablets) during Week 1, 50 mg during Week 2, 75 mg during Week 3, and 100 mg during Week 4.
- Those who weigh >68- \leq 83 kg will titrate from 25 mg daily to 150 mg daily: 25 mg (two 12.5-mg tablets) during Week 1, 50 mg during Week 2, 100 mg during Week 3, and 150 mg (two 75-mg tablets) during Week 4.
- Those who weigh >83 kg will titrate from 25 mg daily to 200 mg daily: 25 mg (two 12.5-mg tablets) during Week 1, 50 mg during Week 2, 100 mg during Week 3, and 200 mg (two 100-mg tablets) during Week 4.

During the treatment phase, the following ecopipam HCl doses will be administered for each of the weight bands:

- Those who weigh $\ge 18 \le 23$ kg will receive 37.5 mg daily.
- Those who weigh >23-\(\le 34\) kg will receive 50 mg daily.
- Those who weigh >34-\(\le 44\) kg will receive 75 mg daily.
- Those who weigh >44-\(\le 68\) kg will receive 100 mg daily.
- Those who weigh >68-\le 83 kg will receive 150 mg daily.
- Those who weigh >83 kg will receive 200 mg daily.

All doses will be administered PO once daily in the evening.

At the end of the open-label treatment phase, subjects will titrate off therapy and receive ecopipam HCl doses that will be reduced by 25 mg/day until off of drug; signs of symptoms of withdrawal will be monitored.

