9.1. Extent of Exposure

Duration of exposure will be summarized using descriptive statistics. The duration of exposure will be categorized in months (<1, 1-<2, 2-<3, 3-<4, 4-<5, 5-<6, 6-<7, 7-<8, 8-<9, 9-<10, 10-<11, 11-<12, \geq 12 months) as well as in days (1-27, 28-55, 56-83, 84-111, 112-139, 140-167, 168-195, 196-223, 224-251, 252-279, 280-307, 308-335, \geq 336). Duration of exposure (months) will be calculated as ((Date of Last Dose – Date of First Dose) +1)/30.25. If date of last dose is unknown, then the date of last clinical visit will be used.

A listing including study drug administration information from the eCRF will be presented.

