9.2. Treatment Compliance

Subjects are expected to take study medication once per day.

Treatment compliance, as a percentage, will be calculated as compliance (%) = (Sum of Study drug taken= Yes) / (number of days in study) x 100. The number of actual doses taken will be recorded on the eCRF.

Subjects will be considered compliant overall for study medication if the compliance is \geq 80%. Descriptive statistics (number of subjects, mean, SD, median, minimum, and maximum) for number of actual tablets taken, number of expected tablets taken, and treatment compliance will be summarized.

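### Exposure is counted as calendar days from first to last dose, so drug-free days before a permitted restart, or in any other interruption, are reported as exposure

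*SAP*

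**What the plan says.** SAP 6.2 sets the rule: "Duration of exposure is defined as (Date of Last Dose – Date of First Dose) +1". SAP 9.1 repeats it for months: "Duration of exposure (months) will be calculated as ((Date of Last Dose – Date of First Dose) +1)/30.25". It then sorts subjects into rows: "The duration of exposure will be categorized in months", and also in days. The top rows are 12 months or more and 336 days or more. Neither section has a term for interrupted dosing.

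Protocol 8.3, and 7.5 in the same terms, says: "Any subject with a new positive response on questions 4 and/or 5 of the C-SSRS will be immediately discontinued and evaluated for risk". The next sentence reads: "Dosing may be restarted at the discretion of the Investigator following consultation with the Sponsor or its designee". Neither section states a maximum gap.

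Two planned outputs carry information on days without drug. SAP 9.2 computes compliance as days with drug taken over days in study, with 80% as the threshold (Table 14.1.6), and adds: "The number of actual doses taken will be recorded on the eCRF". Listing 16.2.5.1 shows study drug administration. Neither feeds the exposure tables.

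On treatment length, protocol 10.5 says: "During the 4-week titration period, the following ecopipam HCl doses will be administered for each of the weight bands". The synopsis then says: "During the 52-week treatment phase, the following ecopipam doses will be administered for each of the weight bands". The synopsis also gives 52 weeks as the duration of treatment.

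**The concern.** The primary objective is long-term safety and tolerability, in a single-arm extension whose size is set by how many subjects complete the parent study. Extent of exposure is therefore the main statement of how much time on drug stands behind the safety tables.

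A first-to-last-dose span equals time on drug only if dosing is continuous. The protocol provides for at least one route by which it is not, and that route is triggered by suicidality, which protocol 13.2.1 lists as an event of special interest. For those subjects the whole off-drug period would be reported as exposure. The same happens with any other interruption. The error runs in one direction only: the span can overstate days dosed but cannot understate them.

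**Working it through.** The documents give no exposure figure to reproduce. The check applies the SAP formula to the planned durations and then removes drug-free days.

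**Inputs**
- Formula and month divisor: SAP 6.2 and 9.1.
- Span: 364 days (52 weeks, synopsis duration of treatment), or 392 days if the 4-week titration is additional. The text does not settle which.
- Month 12 target: Day 337 (SAP 6.4).
- Gap lengths: assumed, because the documents give none.
- Days in study, for compliance: assumed equal to the 364-day span, with full dosing outside the gap.

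**Row boundary.** 12 × 30.25 = 363, so the top month row starts at 363 days.

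**SAP result on a 364-day span.** 364 / 30.25 = 12.03 months, whatever the gap. The subject falls in the ≥12-month and ≥336-day rows.

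**Net result.** Net days = 364 − gap; net months = net days / 30.25; compliance = net days / 364.

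| Assumed gap (days) | Drug-free share of counted days | Net days | Net months | Rows on net figure | Compliance |
|---|---|---|---|---|---|
| 0 | 0% | 364 | 12.03 | ≥12 months; ≥336 days | 100% |
| 30 | 8.2% | 334 | 11.04 | 11 to <12 months; 308–335 days | 91.8% |
| 90 | 24.7% | 274 | 9.06 | 9 to <10 months; 252–279 days | 75.3% |
| 180 | 49.5% | 184 | 6.08 | 6 to <7 months; 168–195 days | 50.5% |

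**Where the rows change (364-day span).** 364 − 2 = 362 is below 363, so a gap of 2 days or more takes the subject out of the top month row. 364 − 29 = 335, so 29 days or more takes the subject out of the top day row.

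**392-day span.** 392 / 30.25 = 12.96 months. A 29-day gap leaves 363 days, still in the top month row. A 30-day gap leaves 362 (11.97 months), out of it.

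**What compliance would reveal.** A 72-day gap gives 292/364 = 80.2% and a 73-day gap gives 291/364 = 79.9%. On this span, gaps of up to 72 days still read as compliant.

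**Completer at the SAP's Day 337.** Even with a 7-day taper (the 200 mg dose reduced by 25 mg each day), the span is about 343 days, and 343 / 30.25 = 11.34 months. This subject is in the top day row but not the top month row, with no gap at all.

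**The case against.** Several points against the concern are sound.

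- **Titration and taper.** A reader might infer that these days also inflate exposure. They do not: subjects take ecopipam on those days, and counting them is conventional. A row for time at maintenance dose would be informative but is optional. It would also need a definition that copes with the one-level dose reduction in protocol 7.4 and the weight-band changes in 10.5.
- **Scope of restart.** A reader might infer that any discontinued subject may return after an unlimited gap. The restart sentence follows only the C-SSRS trigger and requires consultation with the sponsor or its designee. No limit is stated, which is not the same as no limit applying.
- **Adverse event rates.** A reader might infer that event rates are diluted by off-drug time. SAP 9.3 plans numbers and percentages of subjects, with no exposure-adjusted rate. Events during a gap before a restart still count as treatment-emergent. The formula affects the exposure tables only.
- **Visibility.** On the 364-day span, gaps of 90 and 180 days would already fall below 80% compliance.
- **Top month row.** A completer at Day 337 may miss it without any gap, so the effect on that row depends on how long treatment actually runs.
- **Data.** Protocol 9.4 monitors compliance by tablet counts, and SAP 9.2 refers to doses taken. Neither establishes dated daily records.

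These points narrow the concern but leave its core intact. Compliance and the listing let a reader suspect off-drug time; they do not correct the exposure rows, and compliance does not flag the shorter gaps.

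**Conclusion.** The point holds. Followed exactly, SAP 6.2 and 9.1 count drug-free days as exposure. For an affected subject on a 364-day span, the SAP reports 12.03 months against 11.04, 9.06 or 6.08 months net of 30, 90 or 180 off-drug days. These figures rest on assumed gaps and an assumed span. The effect on the study mean is total drug-free days divided by the number of subjects. The documents give neither quantity, and few subjects may be affected. It is a correctable inaccuracy in a supporting table for the primary objective, not a flaw in the adverse event analysis.

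The treatment-length wording is a separate matter. A reader might infer that it shows the exposure formula to be wrong, or that 52 weeks at maintenance dose cannot be reached. The text does not settle that. Titration below the target dose takes 14 days (lowest band) or 21 days (other bands). If titration lies inside the 52 weeks, 364 − 14 = 350 or 364 − 21 = 343 days remain. If it is additional, 392 − 14 = 378 or 392 − 21 = 371 remain. The passages disagree and need reconciling, whatever is done about the formula.

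**What to change.** In SAP 6.2 and 9.1:
1. Keep the calendar span and add exposure net of documented interruptions beside it in Tables 14.1.5 and 14.1.5a. Days recorded as drug taken can serve instead, as far as the eCRF records allow.
2. Base the month and day categories on the net figure.
3. Report n (%) of subjects who stopped and restarted, with gap length.
4. Label this as a post-lock addition in SAP Section 10, where the by-day exposure table is already listed as one.

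Titration and taper stay in total exposure.

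Separately, the sponsor must reconcile:
- the synopsis's 4-week titration plus 52-week treatment phase with its 52-week total duration; with Table 2, which places titration at the start and dispenses only down-titration drug at Month 12; with the SAP's Day 337 target for Month 12; and with top exposure rows that start at 363 days in one table and 336 in the other;
- discontinuation with restart in protocol 7.5 and 8.3. No clinical rule is proposed here.

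The cost is SAP wording, minor reprogramming of two tables, slightly less favourable exposure figures and one more post-lock change. Before committing to gap lengths, check that the eCRF holds stop and restart dates. Protocol 8.3 requires the last-dose date at discontinuation, but no section states that the restart date is recorded.
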